7.6 Multi-center Studies and Pooling of Centers

The study will be conducted at up to 80 clinical trial sites in the US and Canada.

This is a multicenter study and before data from all sites are pooled, the effect of site will be assessed for the secondary efficacy endpoints. A sufficient number of subjects (≥ 7) will be

required within each investigative site to determine if there are any outlying sites. If an investigative site is unable to enroll a sufficient number of subjects, it may be necessary to combine smaller sites (where enrollment is too low to detect differences) to create “pseudo-sites”. Sites with < 7 subjects will be considered eligible for pooling. Eligible sites will be pooled sequentially with other sites in the same region until a sufficient number of subjects are reached (at least seven).

In this process, sites with < 7 subjects will be ordered numerically in ascending order, based on the investigative site number. Sites with < 7 subjects will then be sequentially pooled with other sites in the same region in ascending order by site number until the resulting pseudo-site has at least 7 subjects meeting the PP population definition, thus creating a new “pseudo-site”. The process will begin again with the next sequential small site until all small sites have been pooled with other sites in the same region into a pseudo-site.

7.7 **Multiple Comparisons/Multiplicity**

As this study is not powered for a primary objective, and as descriptive statistics will be used for analysis of the primary objective, no adjustments for multiplicity are required.

7.8 **Examination of Subgroups**

Subgroup analysis of age (< 65 years, \geq 65 years), sex (Female, Male), race group (White, Non-white), ethnicity (Hispanic-Latino, not Hispanic-Latino), site geography (outside the US, Eastern US*, Southern US*, Northern US*, Western US*) and number of previous episodes of CDI recurrence at Baseline will be conducted on the efficacy analysis if a sufficient sample size exists for each subgroup. This analysis will include the ITT and mITT analysis populations to understand any differences.

*States included in the identified US geographical regions are as follows:

- Eastern US: Connecticut, Delaware, District of Columbia, Maine, Maryland, Massachusetts, New Hampshire, New Jersey, New York, Ohio, Pennsylvania, Rhode Island, Vermont, Virginia, West Virginia
- Southern US: Alabama, Arkansas, Georgia, Florida, Kansas, Kentucky, Louisiana, Mississippi, North Carolina, Oklahoma, South Carolina, Tennessee, Texas
- Northern US: Illinois, Indiana, Iowa, Michigan, Minnesota, Missouri, Nebraska, North Dakota, South Dakota, Wisconsin

- Western US: Arizona, California, Colorado, Idaho, Montana, Nevada, New Mexico, Oregon, Utah, Washington, Wyoming

Other subgroups will include subjects with a, medical history of Ulcerative Colitis (UC), Crohn's Disease (CD), and/or Inflammatory Bowel Disease (IBD) which was ongoing at the time of study treatment, and medical history of immunocompromising condition(s) which was ongoing at time of IP administration.

Because immunocompromising conditions may result from medications, diseases, or a combination of both, the following algorithm will be used to identify participants in this subgroup:

Medical History Rules

Standardized MedDRA query (SMO) of Malignant tumours

Search will require at least 2 Broad terms or at least1 narrow term for events which were ongoing at the time of IP administration.

Other Medical History

Preferred Terms (PT), High level Term (HLT), or High Level Group Term (HLGT) will be used to identify the following conditions, which were ongoing at the time of IP administration, based upon the Centers for Disease Control (CDC) guidelines for immunocompromised conditions listed under CDC Pneumococcal Vaccine Recommendations ([Pneumococcal Vaccine Recommendations | CDC](#))

- PT: End Stage Renal Disease
- PT: Renal Failure
- PT: Asplenia
- PT: HIV
- PT: HIV infection
- HLT: Haemoglobinopathies congenital
- HLT: Immunodeficiency syndromes

Concomitant Medications:

Anatomical Therapeutic Chemical (ATC) classification will be used to identify immunocompromising medications taken within the following window: Two weeks prior to the first IP administration to 8 weeks after administration. Only systemic routes of administration will be included such as those taken orally or by injection (intramuscular, subcutaneous, or intravenous); topical medications will be excluded.

- ATC classification H02AB or H02BX – Corticosteroids. These medications must have been taken for 5 consecutive days within the window specified above.
 - As described in the protocol, 20 mg prednisone-equivalent is considered to be an immunocompromising dose. Prednisone equivalent doses are listed in the table below where the dose of the medications below is multiplied by the applicable conversion factor listed in the table (e.g., 4 mgs of Dexamethasone is equivalent to 26.8 mg prednisone)
 - The dosing regimen will be incorporated into a calculation of total daily dose, with a total of 20mg prednisone-equivalent per day as the threshold for immunocompromising.

Preferred Term	Prednisone equivalent conversion factor (multiplication)
Cortisone	0.2
Dexamethasone	6.7
Hydrocortisone	0.25
Methylprednisolone	1.25
Methylprednisolone Sodium Succinate	1.25
Prednisolone	1
Prednisone	1
Triamcinolone	1.25

- ATC classification L01, L03, L04 includes many systemic immunosuppressive medications with varying doses, dosing regimens, routes of administration, and half-lives. Use of any of the medications used two weeks prior to IP administration to 8 weeks after administration will be considered as immunocompromising. **Note:** ATC classification L02 will be excluded since these hormone-based medications are not considered to be immunocompromising.

A final output will include a summary table summarizing the total number of subjects flagged as immunocompromised and a listing detailing the immunocompromised subjects as seen in example Tables 1 and 2.

Example Table 1. Summary information Inflammatory Bowel Disease:

	Ulcerative colitis (UC)	Crohns disease (CD)	Inflammatory bowel disease (IBD)	Total
Number of participants	[number]	[number]	[number]	[number]

Example Table 2. Listing of Immunocompromised Subjects

(Note: listing should include one entry per row to display subjects with multiple SMQ hits in multiple rows)

USUBJID	*SMQ/[B or N]/MHDECOD	CMCLAS/ CMDecod/ CMRoute/ CMDose/CMDoseU/CMDoseFRQ CMDoseEq**
---------	-----------------------	---

*SMQ /[B or N]= Standardized MedDRA Query Broad (B) or Narrow (N)**CMDoseEq=concomitant medication dose equivalent

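### The immunocompromised subgroup is described by status at the enema, but its medication rule lets drugs first started up to 8 weeks afterwards decide membership

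*SAP*

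**What the plan says.** SAP 7.8 (Examination of Subgroups) introduces the subgroup as subjects with a "medical history of immunocompromising condition(s) which was ongoing at time of IP administration". It then notes that such conditions can come from disease, medication or both, and says "the following algorithm will be used to identify participants in this subgroup".

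The algorithm has two limbs.

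- **Medical history.** The malignancy query is limited to terms "for events which were ongoing at the time of IP administration", and the list of other conditions carries the same limit.
- **Medication.** Drug classes are used to find "immunocompromising medications taken within the following window: Two weeks prior to the first IP administration to 8 weeks after administration". For systemic corticosteroids, "These medications must have been taken for 5 consecutive days within the window specified above", "with a total of 20mg prednisone-equivalent per day as the threshold for immunocompromising". For ATC classes L01, L03 and L04 there is no dose or duration condition: "Use of any of the medications used two weeks prior to IP administration to 8 weeks after administration will be considered as immunocompromising".

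SAP 6.6.2.6 summarises AEs and TEAEs by SOC and PT for subjects with and without immunocompromising conditions. SAP 6.10 compares the same two groups for efficacy by chi-square test. SAP 6.6.2.1 presents TEAEs through 6 months and rules out inferential statistics for AE data.

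**The concern.** A subgroup meant to describe who the subjects were at treatment should be fixed by information available at treatment. Under the medication rule, an adverse event in the first 8 weeks that leads to a qualifying drug, or to a corticosteroid dose raised to the SAP's threshold, moves the subject into the immunocompromised group and takes the event along. The subgroup's TEAE rate then rises and the complement's falls, even with no true difference. Subjects who die or leave early have less time to qualify, which pushes the other way for those outcomes.

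The study's stated purpose is safety in a broader population than before, and immune status is one of only two safety splits named in SAP 6.6.2.6. A distorted contrast there could be read as a property of immunocompromised patients.

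**Working it through.** **Can the rule be met wholly after the enema?** Yes. Five consecutive days inside the window, or any L01/L03/L04 use inside it, can fall entirely after treatment. Protocol 7.3.3.2 counts concomitant medication from the first dose onward. Nothing in SAP 6.6.2.6, 6.10 or 7.8 adds a start-date condition. The window has 14 days before and 56 days after the enema, so 56/70 = 80% of it is post-treatment, and that part coincides with the 8-week efficacy period.

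**Could the planned outputs reveal it?** No baseline-only version is specified. Example Table 2 in SAP 7.8 carries dose fields ("CMDose/CMDoseU/CMDoseFRQ") but no start date. The general listings in SAP 6.5 and 7.1 are the other places where post-enema starts might be traced.

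**How large could it be?** The plan states no figure, so this is an illustration.

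Inputs from the documents:
- N = 750, the treatment cap.
- 8-week TEAE rate p = 154/267 = 0.577 and overall rate 178/267 = 0.667, both from study 2017-01 with arms pooled (Protocol 5.3.4).

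Assumptions:
- True immunocompromised share b = 0.15, with no true difference in TEAE rate.
- Probability of a post-enema drug start: c = 0.005 without an 8-week TEAE, and a = 0.01, 0.03 or 0.10 with one.
- The later-TEAE chance among those event-free at 8 weeks is (178 − 154)/(267 − 154) = 0.212, independent of the flag.

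Formulas:
- Subgroup rate = p[b + (1−b)a] / {p[b + (1−b)a] + (1−p)[b + (1−b)c]}
- Complement rate = p(1−a) / [p(1−a) + (1−p)(1−c)]
- 6-month rate = 8-week rate + (1 − 8-week rate) × 0.212
- Subjects moved by events = 750(1−b)pa
- 95% half-width of the 6-month difference = 1.96 × √[(2/3)(1/3)(1/n₁ + 1/n₀)], where n₁ and n₀ are the flagged and unflagged numbers

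Worked case, a = 0.10:
- Subgroup: 0.5768 × 0.235 = 0.1355 and 0.4232 × 0.15425 = 0.0653, so the rate is 0.1355/0.2008 = 67.5%.
- Complement: 0.5191/(0.5191 + 0.4211) = 55.2%. The 8-week gap is 12.3 points.
- At 6 months: 74.4% against 64.7%, a gap of 9.7 points.
- Flagged: 750 × 0.2008 ≈ 151.

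| a | Moved by events | 8-week gap | 6-month rates | 6-month gap | Half-width |
|---|---|---|---|---|---|
| 0.5% (unrelated) | – | 0 | 66.7% vs 66.7% | 0 | – |
| 1% | 4 | 0.8 | 67.2% vs 66.6% | 0.6 | 9.3 |
| 3% | 11 | 3.7 | 69.1% vs 66.2% | 2.9 | 9.1 |
| 10% | 37 | 12.3 | 74.4% vs 64.7% | 9.7 | 8.4 |

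Gaps and half-widths are in percentage points.

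**Sensitivity.** With b = 0.10 the 6-month gaps run from 0.9 to 12.6 points; with b = 0.30, from 0.3 to 5.7. With c raised to 0.03 (b = 0.15) they become −2.4, 0 and 6.9, and the last lies inside its half-width of about 8.3.

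**Deaths** (p = 2/267, c = 0.03, b = 0.15): subgroup 0.64% vs complement 0.77% if no decedent is newly flagged, equal at a = 3%, and 1.00% vs 0.70% at a = 10%.

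**Recurrence** (p = 0.296 from the 70.4% success rate, c = 0.03, b = 0.15): 26.4% vs 30.2% at a = 0, and 36.0% vs 28.1% at a = 10%. With c = 0.005 and a = 0 it is 29.0% vs 29.7%. For both outcomes the sign depends on which subjects start drugs.

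**The case against.** The strongest reply is that the window may be deliberate. In SAP 7.8 the timing phrase attaches to medical history, the next sentence widens the concept to medication, and the window is then stated twice and matches the 8-week efficacy period. SAP 6.6.2.6 and 6.10 put a timing phrase on inflammatory bowel disease only, and neither refers back to 7.8. The SAP also mentions varied regimens and half-lives for L01/L03/L04 drugs.

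This is a fair reading of what the sponsor may have intended, but the SAP does not say it. SAP 7.8 holds the only definition of the subgroup. The remark on half-lives explains why any L01/L03/L04 use is accepted, not why a drug first started after the enema counts, and it does not apply to corticosteroids. Even a deliberate window would let outcomes decide membership.

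The second reply is that the effect is probably small. Much of this stands. The 10% scenario has no support in the documents, and Protocol 5.3.4 reports that 86.1% of TEAEs in the 2017-01 maximum-severity tabulation were mild to moderate. The one 6-month gap in the table that exceeds sampling error depends on the 0.5% background rate. AE tables are not tested and nothing is powered.

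The third reply is that the listings would show post-enema starts and that ad hoc analyses are allowed. That helps a diligent reader, but listings do not correct the subgroup tables, and no baseline-only analysis is committed to.

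**Conclusion.** The concern holds and should be fixed. On its wording, the rule allows a post-treatment event to decide membership of a group described by status at treatment; that part is certain. The size is not known: the documents give no rate of drug starts after the enema. The false 6-month TEAE gap is zero if starts are unrelated to events. It stays well inside sampling error at start rates of 1% to 3% after an event, and slightly exceeds it at 10%, under the assumed 15% share and 0.5% background. None of these is an upper bound. The direction for deaths, early exits and the efficacy comparison is undetermined. The damage is confined to subgroup results; the primary endpoint in the whole Safety Population does not use the flag.

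**What to change.** For the SAP 6.6.2.6 tables and the SAP 6.10 comparison:

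1. Derive the medication flag from use before the first enema only: the same ATC classes, with a recorded start before the enema, and taken in the 2 weeks before it or ongoing at it. Include intermittent regimens already under way.
2. Apply the SAP's existing corticosteroid dose and duration criteria to pre-enema records only, so that neither a later start nor a later dose increase confers membership.
3. State how partial start dates are classified. SAP 5.2.1 leaves their relative day missing, and SAP 7.3 imputes nothing beyond AE data and Cdiff32 scores. One option is to count a start that cannot be placed before the enema only in the sensitivity version.
4. Keep the present window as a labelled sensitivity analysis.
5. Add the drug start day relative to the enema to Example Table 2.

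The cost is SAP wording, a date condition, a partial-date rule, one listing column and one repeat of the subgroup tables. No new data should be needed. Protocol 7.3.3.1 and 7.3.3.2 cover medication from 30 days before the first dose to the end of study, including dose changes, and the present window and 5-day rule already need dated use. Start dates are not named as a field, so this is an assumption.

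The downside is a somewhat smaller subgroup. A few intermittently dosed drugs last given before the 30-day period, or short courses straddling the enema, may be misclassified. The sensitivity analysis shows how much this matters for courses that continue after the enema.

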8 COMPUTER SOFTWARE

All analyses will be performed by Medpace using Version 9.3 or later of SAS® software. All summary tables and data listings will be prepared utilizing SAS® software.
